### **Sample Size**

We request permission to study up to 30 subjects so that we will have 24 evaluable subjects, respectively, with complete sampling at all time periods. Sample size will be divided into 3 groups; young (18-39-year-old) middle (40 – 59-year-old) and older (60 – 75-year-old).

Sample size was determined using of bootstrap analyses and conventional calculations to estimate the pharmacokinetic parameters within the desired level of accuracy. Table 1 shows the results of 1000 bootstrap replications of the original 11 individuals in the pharmacokinetic study, resampled with N = 11 (the original study size) and N = 20. As expected, the estimates are more precise with increasing study size. The mean and 95% confidence intervals are shown for each parameter.

N	Parameter	Mean	95% Confidence Bound		Range	Correction	Corrected Range
			Lower	Upper			
11	Cl1	0.98	0.89	1.08	20%	2.54	50%
	V1	10.2	8.9	11.9	29%		74%
	Cl2	0.21	0.18	0.24	29%		74%
	V2	7.1	6.1	8.1	28%		70%
20	Cl1	0.97	0.95	1.01	7%	1.88	12%
	V1	10.1	9.6	10.6	10%		18%
	Cl2	0.20	0.20	0.21	8%		16%
	V2	7.0	6.7	7.3	8%		16%

**Table 1** Bootstrap parameter estimates of PK model.

The 95% confidence intervals from the bootstrap are corrected to provide a “best” estimate of the true 95% CI using the upper confidence limit (UCL) method of Browne [1]. As described by Whitehead [10], the 95% UCL correction is  $k/\chi_{(0.95,k)}^2$  where k is N-1, the number of degrees of freedom. As seen in Table 1, the parameters estimated for the initial 11 subjects have a reasonable level of certainty (95% CI < 30% of the mean value) for a small study. However, the corrected CI range from the bootstrap for an N=11 study is closer to 70%. A study with 20 subjects will estimate the parameters within a corrected 95% CI range within 20% of the mean estimated value (Table 1, numbers in red). This is sufficient accuracy to inform the subsequent studies.

Sample size in this study is increased to 24 to permit stratifying by age (3 strata), weight (2 strata), and sex. A corrected confidence range less than 20% (Table 1) implies that mixed effect analysis will distinguish covariate effects in the range of 40% in a study with 20 or more subjects. This is the range at which the covariate effect may be clinically consequential. In practice, mixed-effects analysis with NONMEM is often sensitive to covariate effects smaller than predicted by preliminary analyses.

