## Methods and Measures

Equal numbers of adult men and women will be recruited. Sample size will be divided into 3 groups; young (18-39-year-old) middle (40 – 59-year-old) and older (60 – 75-year-old).

Subjects will report to the CTSI Clinical Research Unit (CRU) for two visits, separated by at least 5 days. On study visit one informed consent will be obtained and eligibility verified. Then two intravenous (IV) catheters will be inserted, one in each forearm, with one for drug infusion and the other for blood sampling. After baseline measures, subjects will receive oxytocin (Pitocin®), 14  $\mu$ g (8.2 IU) over 30 minutes. This dose and infusion duration were chosen based on previous studies showing no adverse events in 10 volunteers and our preliminary PK model which predicts that plasma oxytocin concentrations will be above the limit of detection (1 pg/ml) at 120 min. Venous blood samples (5 ml) will be obtained at 2, 5, 10, 20, 30, 40, 50, 65, 90, and 120 minutes after the initiation of oxytocin administration for oxytocin assay.

On study visit 2, one IV catheter will be placed for blood sampling. After baseline measures, subjects will receive 102  $\mu$ g (60 IU) intranasal oxytocin (Tonix-1900, Tonix Pharmaceuticals, Chatham, NJ). Venous blood samples (5 ml) will be obtained at 1, 2, 5, 7, 10, 15, 20, 25, 35, 45, and 60 minutes after the initiation of the oxytocin administration for oxytocin assay. See graph 3 for rationale for the times of sampling.

**Figure 2. A)** PK modeled OXT concentrations in preliminary data compared with published reports. **B)** Fraction of targeted concentration using TCI. 95% prediction intervals from LC/MS or ELISA assays of duplicate samples (n=11).

We will abandon an individual participant's study and schedule another participant should we be unable to successfully place the intravenous catheters.

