## **Interventions and Interactions**

**Study Visit 1:** The participant will report to the Clinical Research Unit (CRU) of the Wake Forest Clinical Translational Science Institute (CTSI), in the morning after having had nothing to eat or drink since midnight. The participant will review and sign the Informed Consent. After informed consent is adequately obtained, a detailed medical history will be obtained from the participant, female participants will have a urine pregnancy test performed to determine pregnancy status. Vital signs to include blood pressure (BP), heart rate (HR), respiratory rate (Resp) and peripheral oxygen saturation (POX) will be measured and recorded along with height and weight.

Once eligibility has been determined; baseline vital signs (BP, HR, Resp, POX) will be obtained for a baseline measurement and then at the following intervals after the infusion has been initiated; 5, 10, 30, 60, 90 and 120 minutes. Two intravenous catheters will be inserted, one in each arm, and baseline measurements will be obtained. Then 14 µg (8.2 IU) oxytocin (Pitocin®), obtained from the research pharmacy, will be infused over 30 min through one of the catheters. Blood (5 ml) will be sampled from the other catheter at 2, 5, 10, 20, 30, 40, 50, 65, 90, and 120 minutes after the initiation of oxytocin, placed on ice, plasma separated in a refrigerated centrifuge, and stored at -80°C until analyzed for oxytocin concentration. The study will not be blinded. The intravenous catheters will be removed after all data collection and the subject discharged from the CRU. The duration for study visit 2 will be approximately 3.5 hours.

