## **Study Visit 2**

On the second visit, the participant will report to the CRU, in the morning after having had nothing to eat or drink since midnight. Baseline vital signs (BP, HR, Resp, POX) will be obtained for a baseline measurement and then at the following intervals after the intranasal oxytocin: 10, 20, 30, 60, 90 and 120 minutes. One intravenous catheter will be inserted. Oxytocin, 102 µg (Tonix-1900, Tonix Pharmaceuticals, Chatham, NJ), obtained from the research pharmacy, will be self-administered in the nasal passages as one metered spray in each nostril followed in 5 min by a second metered spray in each nostril. Blood (5 ml) will be sampled from the IV catheter at 1, 2, 5, 7, 10, 15, 20, 25, 35, 45, and 60 minutes after the initiation of the oxytocin administration, placed on ice, plasma separated in a refrigerated centrifuge, and stored at -80°C until analyzed for oxytocin concentration. The intravenous catheter will be removed after all data collection and the subject discharged from the CRU. The duration for study visit 2 will be approximately 3 hours.

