**Study Stopping Criteria:** Should significant cardiorespiratory or other side effects occur during oxytocin administration, the IV infusion or intranasal self-administration will be stopped and the subject treated as indicated in Treatment of Side Effects. Blood samples will be obtained near the time of oxytocin cessation and according to the sampling intervals of the study once the side effects are successfully treated or resolve.

The study will be stopped if more than 2 individuals exhibit significant cardiorespiratory side effects or after any serious adverse event and future conduct of the study will be determined by recommendations from the DSMC, IRB, and FDA.

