## **Analytical Plan**

The parameters of the PK model will be fit to the observed plasma concentrations using NONMEM. Inter-subject variability (e.g., biological variability) will evaluate additive, proportional, and exponential models. Residual intrasubject variability (e.g., noise) will typically require an additive and multiplicative error model. The influence of covariates (e.g., age, sex, weight) on model parameters will be analyzed by serial inclusion / exclusion, with significance determined by the likelihood ratio test ( $p < 0.01$  if the decrease in  $-2 \log$  likelihood exceeds 6.6 ( $\chi^2_{0.99/2}$ ,  $df = 1$ )). Parameters will be estimated using first-order conditional estimate with  $\eta$ - $\epsilon$  interaction. Covariate effects deemed significant by likelihood ratio test will be validated using jackknife crossvalidation [3]. Jackknife cross-validation provides an estimate of the utility of the covariate to inform the pharmacokinetics in a future individual, rather than merely characterize the pharmacokinetics in the individuals from which the model was derived. The jackknife cross-validation divides the data into  $N$  subsets. Each subset leaves out a single individual. The parameters of the model are re-estimated for each subset with and without the covariate being validated. The inaccuracy (mean  $(|measured - predicted|) / predicted$ ), of the model with and without the covariate is measured in the excluded individual. The covariate is only included in the final model if the improvement in model accuracy in the  $N$  iterations is significantly greater than 0. Jackknife crossvalidation helps compensate for NONMEM's ability to identify very small covariate effects that do not

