meaningfully contribute to accuracy in future patients. We will study 24 subjects. Bootstrap analysis indicates that the confidence interval for studies of 20 individuals using the LC/MS assay will determine the PK parameters with a corrected confidence range < 20%. A corrected confidence range less 20% implies that mixed effect analysis will distinguish covariate effects in the range of 40% in a study with 20 or more subjects. This is the range at which the covariate effect may be clinically consequential. In practice, mixed-effects analysis with NONMEM is often sensitive to covariate effects smaller than predicted by preliminary analyses. The sample size is increased to 24 to provide stratification by age (3 strata), weight (2 strata), and sex. The crossover design permits accurate determination of i.n. bioavailability and dose linearity despite expected high inter-subject variability in absorption.

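### Does counting only completely sampled subjects toward the target of 24 throw away usable pharmacokinetic data?

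*Combined protocol and SAP*

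**What the plan says.** The Sample Size section requests "up to 30 subjects so that we will have 24 evaluable subjects, respectively, with complete sampling at all time periods". It gives no expected loss rate and no derivation of 30. It ties adequate precision to 20 subjects and explains the rise to 24 by stratification on age, weight and sex.

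At visit 1 blood is drawn "at 2, 5, 10, 20, 30, 40, 50, 65, 90, and 120 minutes after the initiation of oxytocin" (Interventions and Interactions), which is 10 samples. At visit 2 the times are "1, 2, 5, 7, 10, 15, 20, 25, 35, 45, and 60 minutes after the initiation of the oxytocin administration" (Study Visit 2), which is 11.

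The Analytical Plan states: "The parameters of the PK model will be fit to the observed plasma concentrations using NONMEM". It later adds "We will study 24 subjects". It has no rule for missed samples and no definition of the analysis set.

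For a subject whose dosing is stopped for side effects, the Study Stopping Criteria under Safety and Monitoring say: "Blood samples will be obtained near the time of oxytocin cessation and according to the sampling intervals of the study", once the side effects have been treated or have resolved. Replacement is described for one case only: Methods and Measures says staff will "schedule another participant should we be unable to successfully place the intravenous catheters", and Volunteer Payment repeats this for visit 1.

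**The concern.** Read together, 30 enrolled, 24 evaluable and 24 studied suggest that anyone without a full profile falls outside the analysis. One missed or failed sample out of 21 would then cost a whole subject, and only six spares are available. That would be wasteful, because a population model does not need complete or equal profiles.

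It could also bias the estimates. Subjects whose dosing is interrupted would have shortened or shifted profiles and would not count as complete. The Background reports that headache and flushing lessened when the same preliminary dose was given more slowly, so a link between side effects and concentration is plausible. If so, dropping these subjects would select on the quantity being estimated.

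**Working it through.** **The plan's figure.** 24/30 = 0.80, so 30 = 24/(1 − 0.20). The figure fits a 20% non-evaluable rate. That rate is back-solved; the documents do not state it.

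**Strict reading.** Evaluable is taken to mean all 10 + 11 = 21 samples present. Assume each sample is lost independently with probability p and no subject drops out. Then P(complete) = (1 − p)^21, and the number complete out of 30 is binomial.

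| p | P(complete) | Expected of 30 | P(at least 24) | P(at least 20) |
|---|---|---|---|---|
| 0.5% | 0.900 | 27.0 | 97% | about 100% |
| 1.0% | 0.810 | 24.3 | 66% | 98% |
| 1.5% | 0.728 | 21.8 | 25% | 83% |
| 2.0% | 0.654 | 19.6 | 6% | 53% |
| 3.0% | 0.527 | 15.8 | 0.2% | 9% |

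Expected completers equal 24 when (1 − p)^21 = 0.8, so p = 1 − 0.8^(1/21) = 1.06%. The chance of reaching 24 is 50% at p = 1.18%. About 1% is therefore a tipping point: at exactly 1%, reaching 24 is still more likely than not.

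**How far the threshold moves.**
- Whole-subject dropout d: p = 1 − (0.8/(1 − d))^(1/21), which is 0.81% at d = 5% and 0.56% at d = 10%.
- Loss by visit, as when a sampling catheter fails: (1 − f)^2 = 0.8 gives f = 10.6% of visits. If half of a failed visit's samples are lost, that is 0.106/2, about 5% of samples. P(at least 24) is 98% at f = 5%, 66% at 10% and 23% at 15%.
- One missing sample of 21 tolerated: the threshold is 3.9%.
- Time periods read as the two visits: the 21-sample calculation no longer applies, and the 20% allowance covers visit-level loss.

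**What exclusion would cost, if it happened.** Of the samples actually drawn, the share belonging to complete subjects is (1 − p)^20, so 18% would be dropped at p = 1% and 33% at p = 2%. At p = 2%, fitting everything uses 630 × 0.98 = 617 of 30 × 21 = 630 scheduled samples. Complete subjects alone supply 630 × 0.654 = 412. Analysing 30 subjects in place of 24 would narrow an interval by at most 1 − √(24/30) = 1 − 0.894, about 11%. This is an upper bound, since partial profiles carry less information and 30 is a ceiling.

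**Whether the plan prescribes exclusion.** The Sample Size sentence says how many complete subjects recruitment should deliver. The sentence that governs the fit refers to observed concentrations and sets no completeness condition. The stopping criteria call for further blood draws after an interrupted dose, which has little purpose if those data are not to be used. The Data Sharing Plan lists dose, sampling times and concentrations for each subject, which are the records needed to fit irregular profiles.

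**The case for a change.** The strongest reply is that the Sample Size section holds the only definition of evaluable in the document, and that the Analytical Plan's "We will study 24 subjects" matches the evaluable count rather than the enrolled one. An analyst could take evaluable as the analysis set, or the choice could be made after the data are seen. The loss rate behind 30 is unstated under any loss pattern. Falling short of 24 would also thin strata that are already small: 24 over three age groups is eight per group, or four of each sex.

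Part of this stands. The analysis set, the handling of missed samples and the meaning of time periods are not written down, and 30 cannot be derived from stated inputs. The charge that data are discarded does not stand, because no section removes an incomplete subject from the fit.

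The bias argument is weak for the same reason. The study also stops if more than two people have significant cardiorespiratory side effects, so few interrupted profiles of that kind could accumulate. Other side effects that interrupt dosing are not capped in this way, but those subjects too continue to be sampled.

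**Conclusion.** The concern does not hold as a defect in the analysis. Its arithmetic is right under its assumptions: 21 samples, independent loss, no dropout and a threshold of 1.06% per sample. Other plausible patterns put the threshold anywhere from about 0.6% to about 5% of samples, and the documents give no loss rate with which to choose among them.

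Missing the complete-profile count would not in itself defeat the precision aim. Taking the plan's statement about 20 subjects as given, at least 20 complete profiles are expected with probability 98% at 1% loss. That falls to 53% at 2%, but incomplete subjects would still contribute to the fit.

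What remains is a gap in detail that analysts fill sensibly. Following the text as written, they would fit every observed concentration with the dose and times recorded for that subject, and the result would be sound. This conclusion rests on reading the Sample Size wording as a recruitment count. The Analytical Plan and the stopping criteria both support that reading, and no section contradicts it.

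### Table 1 corrects the N=20 rows with 19 degrees of freedom although all its variability comes from 11 pilot subjects; k, the scale of the factor and the N=20 widths need correcting together before a 20% precision is claimed

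*Combined protocol and SAP*

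**What the plan says.** The Sample Size section of the combined protocol and SAP bases its precision claim on an earlier study of 11 people. Table 1 reports "1000 bootstrap replications of the original 11 individuals in the pharmacokinetic study, resampled with N = 11 (the original study size) and N = 20". The resulting intervals are then "corrected to provide a “best” estimate of the true 95% CI using the upper confidence limit (UCL) method". The correction is k divided by a chi-square quantile, "where k is N-1, the number of degrees of freedom".

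Table 1 prints a correction of 2.54 for the N=11 block and 1.88 for the N=20 block. The corrected ranges for Cl1, V1, Cl2 and V2 are 50, 74, 74 and 70% at N=11, and 12, 18, 16 and 16% at N=20. From the second set the section concludes: "A study with 20 subjects will estimate the parameters within a corrected 95% CI range within 20% of the mean estimated value".

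The Analytical Plan repeats that 20 subjects measured by LC/MS "will determine the PK parameters with a corrected confidence range < 20" (per cent). Both sections then infer from this threshold that covariate effects of about 40% can be distinguished. The sample size is set at 24 to allow stratification.

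**The concern.** An upper-limit correction of this kind protects against a variance that was estimated from few subjects and may be too small. Its degrees of freedom must therefore be those behind the variance estimate. Drawing 20 records with replacement from 11 people yields no new information on between-subject variance, so the degrees of freedom stay at 10 whatever the resample size. Under the printed rule the correction would shrink towards 1 simply by resampling the same 11 people more heavily.

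At stake is the only quantitative justification of precision in the plan: the 20% figure, which appears in two sections, and the 40% covariate statement drawn from it.

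**Working it through.** **Inputs**, all from the Sample Size section: 11 source individuals; resample sizes 11 and 20; the rule k = N-1; and the means, bounds, ranges and factors in Table 1.

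**1. Reproduce the plan's factors.** The formula is k / (5% lower-tail point of chi-square on k degrees of freedom).
- k=10: 10/3.940 = 2.538 (printed 2.54).
- k=19: 19/10.117 = 1.878 (printed 1.88).

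The opposite-tail reading gives 0.55 and 0.63, so it was not used. The N=20 block therefore uses k=19.

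**2. Reproduce how the factor is applied.** Corrected range = factor × (upper - lower)/mean. For V1 at N=11: (11.9 - 8.9)/10.2 = 29.4%, and 29.4 × 2.538 = 74.6% (printed 74%). For V1 at N=20: (10.6 - 9.6)/10.1 = 9.9%, and 9.9 × 1.878 = 18.6% (printed 18%). The plan thus multiplies the interval width by the factor itself.

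**3. Change only k.** Apply 2.538 to the N=20 widths in the plan's own way:

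| | From printed bounds | From printed range |
|---|---|---|
| Cl1 | 15.7% | 17.8% |
| V1 | 25.1% | 25.4% |
| Cl2 | 12.7% | 20.3% |
| V2 | 21.8% | 20.3% |

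Rounding in the table matters. For V1 the most favourable rounding is (10.55 - 9.65)/10.15 × 2.538 = 22.5%, still above 20%. For V2 it runs from 0.5/7.05 × 2.538 = 18.0% to 0.7/6.95 × 2.538 = 25.6%, so V2 is borderline. For Cl2 the printed bounds (0.20 to 0.21, mean 0.20) give a 5% width against a printed range of 8%. Two-decimal rounding could hide that difference, because the true width may be anywhere up to 0.02/0.20 = 10%.

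**4. Coverage.** Assume roughly normal subject-level parameters and a variance on 10 degrees of freedom. A variance multiplier c covers P(chi-square on 10 df ≥ 10/c).
- 1.878 on the variance: 10/1.878 = 5.325, coverage 86.8%.
- 1.878 on the width, equal to 1.878² = 3.527 on the variance: 10/3.527 = 2.835, coverage 98.5%.
- 2.538 on the width, equal to 6.441 on the variance: coverage 99.9%.

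**5. Put the factor on the right scale.** A width is proportional to a standard deviation, so it needs sqrt(2.538) = 1.593. Applied to the printed N=20 widths (bounds or ranges) this gives Cl1 9.9-11.2%, V1 15.8-15.9%, Cl2 8.0-12.7% and V2 12.7-13.7%. All are below 20%.

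**6. Check the N=20 widths.** Relative to the N=11 widths they are 0.32, 0.34, 0.17 and 0.30 from the bounds (Cl1, V1, Cl2, V2), or 0.35, 0.34, 0.28 and 0.29 from the printed ranges. Resampling the same people at a larger size should shrink widths by about sqrt(11/20) = 0.742. Even with all rounding taken in the plan's favour, the ratios reach only 0.40, 0.39, 0.44 and 0.38.

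Scaling the N=11 widths from the bounds (19.4, 29.4, 28.6, 28.2%) by 0.742 gives:

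| | Uncorrected, N=20 | × 1.593 (k=10) | × 1.370 (k=19) |
|---|---|---|---|
| Cl1 | 14.4% | 22.9% | 19.7% |
| V1 | 21.8% | 34.7% | 29.9% |
| Cl2 | 21.2% | 33.8% | 29.0% |
| V2 | 20.9% | 33.3% | 28.6% |

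At 24 subjects, scaling by sqrt(11/24) = 0.677 with k=10 gives 20.9, 31.7, 30.8 and 30.4%.

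**The case against.** The strongest reply is that changing k alone does not improve the table. Because the plan multiplies a width, 1.88 is already larger than the 1.59 that a 95% limit on 10 degrees of freedom requires. Replacing it with 2.54 on the width would move coverage from 98.5% to 99.9%, further from the target. This stands, and it is why k and the scale must be changed together.

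For the same reason, a reader might infer that the printed corrected ranges cover only 87% and also that the 20% criterion fails. The documents do not support both at once: 87% requires the factor to act on a variance, while the failure in step 3 requires it to act on a width. Nor do they support saying that three of the four parameters fail: only V1 clearly does, V2 is borderline, and Cl2 depends on which printed figure is used.

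A second reply is that k = N-1 may be meant as a projection of the interval that a future 20-subject study would report on its own 19 degrees of freedom. The wording permits that reading. It would, however, leave the uncertainty of the 11-person variance unaddressed, and the section should then say so. What the two cited method papers prescribe for k cannot be checked from the documents.

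A third reply is that the narrow N=20 widths matter more than k. That is also fair: with the scaled widths and k=19, three parameters already exceed 20%. The choice of k then adds 16% to each corrected width (1.593/1.370) and takes Cl1 from 19.7% to 22.9%.

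**Conclusion.** The degrees of freedom in the N=20 block are wrong for an upper-limit correction of a variance estimated from 11 people. The factor should be 2.54 on the variance, or 1.59 on a width, in both blocks. Under the plan's own arithmetic this takes V1 to about 25% and V2 to 20-22%, so the claim of 20% for the parameters as a group does not hold as calculated.

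Whether 20% is achievable depends on the uncorrected N=20 widths. If they are right as printed, the properly scaled correction leaves every parameter at 8-16% and the claim survives. If they should follow sqrt(11/20), all four parameters lie at about 23-35%. That scaling is an assumption, since the bootstrap output is not in the documents, but rounding cannot explain the gap.

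The precision claim is therefore unsupported at present rather than shown to be false, and the 40% covariate statement inherits that status. The point does not show that 24 subjects are too few, and it changes no study procedure.

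**What to change.** In the Sample Size section:
- Define k as the number of pilot subjects minus 1 (10) and use it for both blocks of Table 1.
- State that the factor is a variance factor, and apply its square root (1.59) to confidence-interval widths.
- Recheck the N=20 bootstrap bounds against the output, including Cl2, whose printed bounds and range disagree.
- Recompute the Corrected Range column for both blocks.

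Then restate the 20% claims and the 40% covariate statement, in both Sample Size and Analytical Plan, at the values obtained. Keep the sample size at 24.

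The cost is one recalculated table and a few sentences, with possibly less favourable stated precision. No additional subjects or procedures are needed.

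### Table 1 widens confidence-interval widths by a variance factor instead of its square root, so the N=11 corrected range for V1, Cl2 and V2 is about 45%, not about 70%

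*Combined protocol and SAP*

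**What the plan says.** The Sample Size section bases its precision argument on 1000 bootstrap replications of the 11 pilot subjects, resampled at N=11 and at N=20. It then adjusts the intervals: "The 95% confidence intervals from the bootstrap are corrected to provide a" better approximation of the true interval, using an upper-confidence-limit method. The adjustment is given as a formula: "the 95% UCL correction is $k/\chi_{(0.95,k)}^2$ where k is N-1, the number of degrees of freedom".

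Table 1 prints one factor per block, 2.54 at N=11 and 1.88 at N=20, and a corrected range for each parameter. Two of the N=11 rows read "11 Cl1 0.98 0.89 1.08 20% 2.54 50" and "V1 10.2 8.9 11.9 29% 74" (the last figure in each is a percentage).

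Two statements are drawn from that column. For the pilot size: "However, the corrected CI range from the bootstrap for an N=11 study is closer to 70" per cent. For the larger size: "A study with 20 subjects will estimate the parameters within a corrected 95% CI range within 20% of the mean estimated value". The Analytical Plan repeats the second, saying that studies of 20 individuals "will determine the PK parameters with a corrected confidence range < 20" per cent. Both sections infer from this that covariate effects of around 40% can be distinguished.

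**The concern.** If s² is a sample variance on k degrees of freedom, then k·s²/σ² follows a chi-square distribution with k degrees of freedom. Dividing k by the lower 5% quantile therefore gives a one-sided 95% upper limit for σ²/s², a ratio of variances. The quantity being corrected in Table 1 is the width of a confidence interval, which is proportional to a standard deviation. Its upper limit is obtained with the square root of that ratio. The section mentions no square root and gives no reason for leaving one out.

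The corrected column is the only quantitative justification of sample size that the document shows. It carries the contrast between N=11 and N=20, the 20% precision claim and, through that claim, the 40% covariate statement. If the factor is on the wrong scale, the printed error bars are wrong and the step from precision to detectable covariate effect has to be checked again.

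**Working it through.** **Inputs** (all from Sample Size, Table 1 and its text). Factor k/chi-square with k = N−1. Printed ranges (interval width as a percentage of the mean): 20, 29, 29, 28% at N=11 and 7, 10, 8, 8% at N=20, for Cl1, V1, Cl2 and V2 in that order.

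**Step 1: reproduce the printed factors.** The lower 5% chi-square quantiles are 3.940 (k=10) and 10.117 (k=19).

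- N=11: 10/3.940 = 2.538, printed 2.54.
- N=20: 19/10.117 = 1.878, printed 1.88.

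**Step 2: confirm how the factor was applied.** Printed range times unrooted factor:

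- N=11: 20 × 2.54 = 50.8; 29 × 2.54 = 73.7 (twice); 28 × 2.54 = 71.1. Printed: 50, 74, 74, 70.
- N=20: 7 × 1.88 = 13.2; 10 × 1.88 = 18.8; 8 × 1.88 = 15.0 (twice). Printed: 12, 18, 16, 16.

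The differences fit rounding of the printed ranges. For example, Cl1 at N=20 implies a factor between 11.5/7.5 = 1.53 and 12.5/6.5 = 1.92, which includes 1.88 and excludes the rooted 1.37. The rooted factor reproduces none of the eight corrected ranges. The unrooted factor was applied directly to the widths.

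**Step 3: apply the square root at N=11.** √2.538 = 1.593.

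| Parameter | Printed range | Printed corrected range | Range × 1.593 |
|---|---|---|---|
| Cl1 | 20% | 50% | 31.9% |
| V1 | 29% | 74% | 46.2% |
| Cl2 | 29% | 74% | 46.2% |
| V2 | 28% | 70% | 44.6% |

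Starting from the printed bounds instead of the rounded ranges gives 30.9, 46.9, 45.5 and 44.9%, so the result does not depend on rounding. The printed N=11 figures are too wide by a ratio of 2.538/1.593 = 1.59.

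**Step 4: does the 20% claim at N=20 survive on the printed widths?** Two values of k are considered, because the N=20 block resamples the same 11 people.

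- k=19, factor √1.878 = 1.370: 9.6, 13.7, 11.0, 11.0%.
- k=10, factor 1.593: 11.2, 15.9, 12.7, 12.7%.

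All stay below 20%.

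**Step 5: why these N=20 values should not simply be inserted.** If width falls with the square root of sample size, the N=11 ranges should shrink by √(11/20) = 0.742, to 14.8, 21.5, 21.5 and 20.8%. The table prints 7 to 10%. Applying the rooted factors to the scaled widths gives:

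- k=19: 20.3, 29.5, 29.5, 28.5%.
- k=10: 23.6, 34.3, 34.3, 33.1%.

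Square-root scaling is an assumption here, not a figure from the document. It shows that the N=20 rows need their own check before a new corrected column is printed.

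**The case against.** The best defence is that nothing the protocol concludes is reversed. The error widens the intervals, the less-than-20% statement remains true on the printed N=20 widths, and about 45% at N=11 is still well above 20%. That stands, and it limits the point to a correction of the justification. A reader might go further and infer that the sample size is wrong, or that the trial is larger than it needs to be. The document does not support this: the step from 20 to 24 is explained by stratification on age, weight and sex, and the section also cites conventional calculations that it does not show.

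A reader might also infer that the protocol rejects N=11 as inadequate on the strength of the 70% figure. It does not say so. It describes the pilot estimates as reasonably certain for a small study and then reports the corrected range.

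The section's description of the corrected interval as a best estimate could be criticised, since an upper limit is not a best estimate. That has little force, because the word is set in quotation marks and the same sentence names the upper-confidence-limit method.

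Finally, the chi-square result is for the variance of a normal sample, whereas these are bootstrap intervals for NONMEM parameters. V1 at N=11 is visibly asymmetric: 1.3 below the mean and 1.7 above. That makes 45% approximate. It does not rescue the unrooted factor, which rests on the same theory.

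**Conclusion.** The correction in Table 1 is on the wrong scale, and the corrected ranges are overstated. At N=11 the factor should be 1.59. The corrected ranges are then about 32% for Cl1 and about 45-46% for the other three parameters, and the 70% sentence should give about 45%. This takes the printed N=11 widths and k=10 as given and uses the chi-square theory that the protocol itself invokes.

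At N=20 the printed figures are also too high for the printed widths, by a ratio of 1.37 with k=19 or 1.878/1.593 = 1.18 with k=10. No replacement values should be taken from that arithmetic until the widths and the degrees of freedom are confirmed. Resampling 20 from 11 people adds no information about the between-subject variance, so k=10 may be the right choice.

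The scale error alone is conservative. It does not overturn the less-than-20% claim or the choice of 24 subjects. Whether that claim survives a check of the N=20 widths is a separate question, which the printed table cannot settle. The correction should be made, but it is not a barrier to running the trial.

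**What to change.** In Sample Size:

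- State the correction to an interval width as the square root of k/chi-square.
- In the N=11 block, replace 2.54 by 1.59 and the corrected ranges by about 32, 46, 46 and 45%, preferably recomputed from unrounded output.
- Change 70% to about 45% in the sentence on the pilot size, noting that Cl1 is lower.
- Recompute the N=20 block from the unrounded bootstrap output with the square-root factor. First confirm that the 7 to 10% widths are correct, and state whether k is 10 or 19 and why.

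Then check that the less-than-20% statement and the 40% covariate statement, in both Sample Size and Analytical Plan, still follow from the recomputed table. If they do, the Analytical Plan wording can stand, since it prints only the bound. If they do not, restate them.

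The cost is one table column, a few sentences and a look back at the existing bootstrap output. No change to enrolment or conduct is requested.
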